## Statistical Analysis Plan

BAY 94-9027 / 19764

Page: 9 of 17

End of treatment is defined as date of latest infusion plus 7 days or end of study, whatever is earlier.

### 24-hour rule:

All bleeds that occur during the same calendar day will be considered as one bleed. Priority will be determined according to the following order:

- - spontaneous bleed
- - joint bleed
- - treated bleed
- - earliest bleed

The analyzed bleed will be the one with the highest priority. It will get the following derived characteristics:

- - combination of all types and locations
- - highest treated status (i.e. treated if at least one bleed on that day is treated)
- - worst assessment of hemostasis

All other bleeds on the same calendar day will not be considered for analysis but only listed.

### 72-hour rule:

A spontaneous joint or spontaneous muscle bleed will not be counted if it occurs within 72 hours of a bleed (or infusion for that bleed) at the same site. For a spontaneous bleed to be affected by this rule, all sites listed on the bleed must also be specified in the previous bleeds during a 72 hour time frame. Infusions for such bleeds will be considered to be follow-up infusions. If the current and previous bleeds are both skin/mucosa bleeds, this rule does not apply. The rule operates with date/time and bleed locations adjusted by 24-hour rule. Bleeds eliminated by 24-hr rule are not considered.

### Joint bleed:

Joint bleeds can occur in more than 1 joint site. When counting sites for the joint bleeds, all sites will be counted. Data reflecting joint site frequencies will include the frequencies over all sites.

### Incremental recovery:

FVIII levels measured by the chromogenic assay will be analyzed.

Incremental recovery is calculated as shown below:

Incremental recovery = (post-infusion FVIII level – pre-infusion FVIII level) \* weight / dose (in IU)

The most recent weight measurement at time of blood sampling will be used for calculation.

If a FVIII level value is below the lower limit of quantification (LLOQ), a data point with the value of one-half the LLOQ will be substituted.

## Statistical Analysis Plan

BAY 94-9027 / 19764

Page: 10 of 17

Participants with positive FVIII inhibitor or any positive anti-drug antibody measurement during study will be excluded from recovery analyses. Results of these participants will be listed.

A validity flag for incremental recovery values will be created. All incremental recoveries will be considered valid except when the following conditions apply:

- Pre-infusion FVIII level is equal to or higher than the post-infusion FVIII level
- Post-infusion FVIII value is below the LLOQ
- The time from previous study drug infusion to the pre-infusion FVIII level measurement is less than 72 hours (i.e. protocol defined wash-out period of 72 hours was not kept)

If an incremental recovery is flagged as not valid, then the corresponding pre-infusion, post-infusion and incremental recovery value will not be considered in tables displaying summary statistics of incremental recovery values and FVIII levels. FVIII levels that are not valid for calculation of incremental recovery will be listed.

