### 4. Study Design

#### 4.1 Overall Design

The study will be a multicenter, single group, uncontrolled open label trial. Severe hemophilia A patients, age  $\geq 18$  years, will be enrolled and treated with prophylaxis treatment and for breakthrough bleeds for at least 100 ED, which may require 1-2 years depending on the

prophylaxis regimen. Assessment of immunogenicity/safety will be performed at pre-defined ED as required by EMA FVIII Guideline.

The recommended starting dose is every 5 days treatment (45 IU/kg)- An assessment of response to treatment will be performed at the next scheduled visit after 10-15 ED (8-10 weeks). Thereafter, participants may be assigned to different dosing regimens (every 7 days or 2x/week) or continue with every 5 days regimen, according to individual bleeding tendency and needs at investigator's discretion. Clinical general safety, efficacy, and immunogenicity will be assessed at baseline, after 10-15 ED, 50-75 ED and after approximately 100 ED.

This study will address regulatory requirements of assessment of safety in a total of 200 participants with 100 ED including pre-licensure participants of the development program from the studies #13024 Protect VIII and #15912 Protect Kids. This study will include at least 25 participants for fulfillment of the requirement and provide a pooled analysis of all clinical studies (phase III/IV) including at least 200 participants observed for at least 100 ED.

The study will assess the important identified risks of development of Factor VIII (FVIII) inhibitors, hypersensitivity, and potential lack of drug effect associated with anti-polyethylene glycol (PEG) antibodies during the first exposures to Jivi and long-term treatment up to 100 ED.

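### The SAP's recovery tables leave out every antibody-positive participant and every absent recovery, so these tables (though not the listings) cannot show antibody-associated loss of effect.

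*SAP*

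**What the plan says.** SAP 4.5 (Incremental recovery) computes recovery as the rise in chromogenic FVIII level times body weight over dose. For a level below the LLOQ, "a data point with the value of one-half the LLOQ will be substituted".

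Two filters follow.

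- Participant level: "Participants with positive FVIII inhibitor or any positive anti-drug antibody measurement during study will be excluded from recovery analyses". The next sentence adds: "Results of these participants will be listed".
- Sample level: a recovery is flagged not valid under any of three conditions. Two concern the result itself: "Pre-infusion FVIII level is equal to or higher than the post-infusion FVIII level" and "Post-infusion FVIII value is below the LLOQ". The third is a gap of less than 72 hours since the previous infusion. The pre-infusion, post-infusion and recovery values of a flagged sample "will not be considered in tables displaying summary statistics of incremental recovery values and FVIII levels". The SAP adds: "FVIII levels that are not valid for calculation of incremental recovery will be listed".

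SAP 6.2 displays pre- and post-infusion levels and recovery by visit and overall, the overall figure being built from each participant's mean across visits. The default set is the mITT, which needs at least 3 months of data.

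On the protocol side, section 4.1 says that the study will assess the "potential lack of drug effect associated with anti-polyethylene glycol (PEG) antibodies". Section 8.2.1 treats low FVIII levels and poor recovery as signs of lost efficacy and mentions 1.5 IU/dL per IU/kg as a mark of reduced recovery. Section 8.3.7 requires loss of efficacy to be documented by levels before and after an injection. Section 9.4.1 plans a summary of incremental recovery and mentions no antibody exclusion.

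**The concern.** Both filters depend on the result, or on something closely tied to it. The participant-level rule removes the people in whom antibody-associated loss of effect could occur. The sample-level rule removes recoveries that are absent. A table built this way will look normal whether or not the drug lost effect in a few people.

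The participant-level rule is also wider than its purpose needs. It acts on any positive result, although Protocol 8.2.1 requires a second sample before an inhibitor is accepted and has ADA-positive samples characterised for neutralising activity. It has no time limit. Recovery is scheduled at Baseline, Visit 3 and the Last Visit (Protocol 8.1.2), so a participant first positive at the Last Visit also loses two recoveries obtained before any antibody was found.

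At stake is how a reader of the study report interprets mean recovery and the pre- and post-infusion levels. No hypothesis test depends on it, and neither does the primary endpoint.

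**Working it through.** The documents give no figure that rests on these rules, so there is nothing to reproduce. The check applies the rules to example values and then sizes the effect.

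**1. What the validity flag removes.** Inputs: dose 45 IU/kg (the recommended starting dose) and LLOQ 1 IU/dL (assumed; the documents do not state it). Recovery = (post − pre) / 45, after replacing values below LLOQ by 0.5.

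| Pre / post (IU/dL) | Recovery | Flag |
|---|---|---|
| 0 / 0 | (0.5 − 0.5)/45 = 0 | not valid |
| 0 / 0.9 | (0.5 − 0.5)/45 = 0 | not valid |
| 3 / 3 | 0 | not valid |
| 3 / 2.9 | −0.1/45 = −0.002 | not valid |
| 0 / 1.1 | (1.1 − 0.5)/45 = 0.013 | valid |
| 0.2 / 5 | (5 − 0.5)/45 = 0.10 | valid |
| 3 / 10 | 7/45 = 0.16 | valid |
| 1 / 60 | 59/45 = 1.31 | valid |

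The flag removes absent recovery, but it keeps reduced recovery. With a pre-infusion level of 0, the LLOQ condition reaches true recoveries below LLOQ/dose. Over an assumed LLOQ of 0.5 to 5 IU/dL and doses of 40 to 60 IU/kg, that runs from 0.5/60 = 0.008 to 5/40 = 0.125, far below 1.5. The LLOQ/2 substitution still serves pre-infusion levels. For post-infusion levels it never reaches a summary table, because those samples are flagged.

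**2. What the participant-level rule removes.** It removes all recoveries of any participant with a positive inhibitor or ADA result, at any value and any visit. The last four rows above would stay for an antibody-negative participant and go for an antibody-positive one.

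**3. Size.** Assume n = 25, of whom k are antibody-positive with recovery 0 at every visit, and mean recovery m in the rest.

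- Mean under the SAP rule: m, whatever k is.
- Mean with everyone kept: m(25 − k)/25.
- Overstatement: 25/(25 − k) − 1, which does not depend on m.

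| k | Overstatement | Mean, all kept (m = 2.5, assumed) | Below 1.5, all kept (exact 95% CI) | Below 1.5, SAP rule |
|---|---|---|---|---|
| 1 | 25/24 − 1 = 4.2% | 2.40 | 1/25 = 4% (0.1 to 20.4%) | 0/24 |
| 2 | 25/23 − 1 = 8.7% | 2.30 | 2/25 = 8% (1.0 to 26.0%) | 0/23 |
| 3 | 25/22 − 1 = 13.6% | 2.20 | 3/25 = 12% (2.5 to 31.2%) | 0/22 |

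The last two columns take everyone else to be above 1.5.

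For the overall table these percentages are ceilings. If one participant had recovery m at Baseline and 0 at the other two visits, his average would be m/3. The all-participant mean would be m(24 + 1/3)/25 = 0.973m, and the overstatement 1/0.973 − 1 = 2.7%. If the excluded participants have normal recovery, there is no upward bias and the rule only discards data.

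**The case against.** A reader might infer that the plan conceals loss of effect, or that every such case vanishes. The documents do not support that.

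- Protocol 8.3.7 makes loss of efficacy an adverse event of special interest, and SAP 6.4 tabulates those events.
- SAP 6.4 gives frequency tables for confirmed inhibitors and for anti-drug and anti-PEG antibodies. For each participant of this study with a positive result, it lists the antibody measurements with recovery results and the number of exposure days. With about 25 to 30 participants, that listing is readable person by person.
- Low but measurable recoveries in antibody-negative participants stay in the table. It is therefore also wrong to say that any near-zero recovery is called invalid, or that the table describes only people in whom the drug worked.

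It can further be said that few cases are likely. Protocol 2.3 reports no new or confirmed inhibitors in the clinical studies and places the anti-PEG response mainly in children under 6, whereas this study enrols adults. Recovery is among the other pre-specified endpoints of a descriptive study, and a table restricted to antibody-negative participants with valid samples is a legitimate display.

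All of this stands, and it keeps the point minor. It does not fully answer it. The listings give no denominator, no comparison by antibody status and no count of low recoveries, and the event table depends on cases being recognised and reported. Protocol 9.4.1 did not plan the restriction.

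**Conclusion.** The point holds for the summary tables only. By construction they cannot show antibody-associated or absent recovery. Their mean is biased upward to the extent that the removed values are low, with the ceilings of 4.2%, 8.7% and 13.6% for 1, 2 and 3 of 25 participants. Those ceilings rest on assumed case numbers and on zero recovery at every visit; the real effect may be smaller or nil.

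Two readings affect the scope. The antibody exclusion names recovery analyses; I take the accompanying pre- and post-infusion levels to fall under it, since SAP 6.2 displays them together. Whether a participant positive only for anti-PEG antibodies is excluded is not explicit: Protocol 8.2.1 groups antibodies to Jivi and/or PEG as ADA, while SAP 4.3 and 6.4 name anti-drug and anti-PEG antibodies separately.

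The study can still report loss of effect through its listings and adverse event tables. Minor severity; a cheap improvement.

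**What to change.** In SAP 4.5 and 6.2:

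- Add a recovery summary of all treated participants who have recovery samples with correct timing. Use treated participants rather than the mITT: Protocol 8.3.7 says that the reported events occurred within the first 4 exposure days, so an early case might not reach 3 months of data.
- Show it overall and by antibody status: never positive; positive, before the first positive result; positive, from the first positive result on.
- Keep recoveries with no rise, and keep post-infusion values below LLOQ as LLOQ/2, unless a dosing or sampling error is documented.
- Report the number and proportion below 1.5 IU/dL per IU/kg, the figure in Protocol 8.2.1.
- Keep the present table, labelled as antibody-negative participants with valid samples only.
- State whether positives for anti-PEG antibodies alone count as ADA.

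The cost is SAP wording and one more table from data already collected. The all-participant mean will be slightly lower and more variable, and the antibody-positive rows may hold very few people.

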**8.1.2 Incremental Recovery of Jivi**

Blood samples for Jivi trough (predose) and recovery levels (15-30 min post injection) will be collected in all participants. Incremental recovery will be determined by collecting a sample for FVIII level before the scheduled injection, and a second sample collected 15-30 min after end of the injection. The exact sampling times before and after injection and the dose administered will be documented in the CRF. Incremental recovery of Jivi is determined by measuring FVIII activity.

Injections given at study visits will be recorded in the site participant records, which will be the source documents and will be used to enter this information in the CRF.

The samples will be collected as described in detail in the laboratory manual. All samples will be processed in the central laboratory. Plasma concentrations of FVIII will be measured using a validated FVIII activity assay ("chromogenic assay").

Samples for incremental recovery should be collected on days when the next prophylactic injection is scheduled and at least 72 h after the prior injection has been given. The measurements should only be performed when the participant is not actively bleeding.

Recoveries should be performed using the participants assigned treatment dose, rounded to full vial size.

Samples will be collected at Baseline, Visit 3 (Week 8-10), and Last Visit, or in case of suspicion of loss of efficacy (LoE)/hypersensitivity and at additional time points based on the investigator's discretion.

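### The SAP validity rule for incremental recovery checks the protocol's 72-hour washout but not its 15-30 minute post-injection window, so a late post sample counts as valid

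*SAP*

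**What the plan says.** Protocol 8.1.2 defines incremental recovery from a pre-injection sample and "a second sample collected 15-30 min after end of the injection". The same window appears in the Schedule of Activities and in the descriptions of Baseline, Visit 3 and the Last Visit (Protocol 10.4). Section 8.1.2 also asks for at least 72 hours since the prior injection, and adds: "The measurements should only be performed when the participant is not actively bleeding". On data capture it says: "The exact sampling times before and after injection and the dose administered will be documented in the CRF".

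SAP 4.5 computes recovery as (post level − pre level) × weight / dose. It then sets a validity flag: "All incremental recoveries will be considered valid except when the following conditions apply". There are three conditions. The first is that the pre level is not below the post level, and the second that the post level is under the LLOQ. The third concerns the washout: "The time from previous study drug infusion to the pre-infusion FVIII level measurement is less than 72 hours". For this one, the SAP gives as its reason that the protocol's washout was not kept. The consequence of the flag is stated next: "If an incremental recovery is flagged as not valid, then the corresponding pre-infusion, post-infusion and incremental recovery value will not be considered in tables". Separately, participants with a positive inhibitor or anti-drug antibody result are excluded from the recovery analyses altogether. SAP 6.2 reports FVIII levels and recovery by visit and as participant means across visits.

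**The concern.** The list is closed, because anything not named in it is valid by rule. The SAP's own reason for the washout exclusion is that a protocol sampling condition was breached. It applies that principle to the washout but not to the post-injection window, although the window is what makes the second sample a recovery measurement.

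The two conditions also differ in what the formula can absorb. With a short washout there is residual FVIII in the pre sample, and the subtraction largely removes it. With a late post sample, FVIII has already declined from its post-injection level, and nothing in the formula restores it. The bias is downward.

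At stake are the by-visit and overall summaries of recovery and of FVIII levels, mainly the minimum, lower quartile and SD in a study of 25-30 participants.

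**Working it through.** **1. Protocol conditions against the SAP flag.** The documents give no figure on this point to reproduce, so the main check is a comparison of text.

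| Protocol 8.1.2 condition | In the SAP 4.5 validity list? |
|---|---|
| At least 72 h since prior injection | Yes |
| Post sample 15-30 min after end of injection | No |
| Not actively bleeding | No |

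The other two SAP exceptions (pre at or above post; post below LLOQ) are plausibility checks. Decline over a few hours would rarely bring the post level down to the pre level or below the LLOQ, so they do not stand in for a window check. No other SAP section adds one. SAP 4.6 (validity review) covers deviations, validity findings and analysis-set assignment, and contains no rule for individual recovery values.

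**2. Number of values.** Recovery is scheduled at Baseline, Visit 3 and the Last Visit. With 25-30 participants that is 25 × 3 = 75 to 30 × 3 = 90 scheduled recoveries, before dropouts and exclusions.

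**3. Size of the bias for one value.** The documents give no half-life. I assume mono-exponential decline with half-life T of 8-20 h, and a negligible pre-infusion level; a residual pre level would make the proportional shortfall in recovery somewhat larger. For a sample at t hours instead of 0.5 h, the end of the window:

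percent change = 100 × (2^(−(t − 0.5)/T) − 1)

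| Time of post sample | T = 8 h | T = 12 h | T = 16 h | T = 20 h |
|---|---|---|---|---|
| 1 h | −4.2% | −2.8% | −2.1% | −1.7% |
| 2 h | −12.2% | −8.3% | −6.3% | −5.1% |
| 4 h | −26.2% | −18.3% | −14.1% | −11.4% |

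Example: t = 2, T = 12 gives 2^(−1.5/12) − 1 = −8.3%.

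**4. Size of the bias for a visit mean.** If m of 25 values are each low by a fraction x, and true values are similar, the mean shifts by −100 × m × x / 25 percent. One value 5% low gives −0.2%; three values 15% low give −1.8%; five values 25% low give −5.0%.

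**5. Can the checks be programmed?**

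- *Window.* Exact sampling times go into the CRF (Protocol 8.1.2). The window runs from the end of injection, and the protocol does not say explicitly that an end time is recorded. SAP 4.3 imputes a missing in-hospital infusion time as the pre-sample time plus 1 minute, or as 10:00. Against an imputed time, a correctly timed sample could fail and a late one could pass.
- *Active bleeding.* The bleeding-episode fields in Protocol 8.1.1 give onset date and time, type, location, intensity, treatment and response. They give no end time, so whether a bleed was ongoing cannot be derived without a proxy rule.

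**The case against.** The strongest case against is that this matters little. Incremental recovery is the last of the other pre-specified endpoints in SAP Table 2-1. The primary endpoint is inhibitor development, ABR is the main efficacy endpoint, and all analyses are descriptive. The injections are given in hospital with the post sample specified for the same visit, and nothing in the documents suggests delays of hours. The SAP reports medians and quartiles, which resist a few low values. The SAP change history shows that the recovery validity rules were specified deliberately in version 2, and the validity review offers a route for gross errors. All of this stands as a limit on importance. It does not close the gap: no reason is given for leaving out the window, and removing a value at review that the SAP calls valid would be a decision made after seeing the data.

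A reader might infer three stronger claims that the documents do not support.

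- **That the flag could cause a normal responder to be handled as having reduced recovery.** The level of 1.5 IU/dl per IU/kg in Protocol 8.2.1 belongs to the investigator's work-up of suspected loss of efficacy or hypersensitivity during the study. The SAP flag only decides what enters tables, and the SAP has no analysis against that level.
- **That recovery is the study's measure of drug effect.** Its place in the endpoint hierarchy says otherwise.
- **That active bleeding should be a programmed exclusion in the same way.** The protocol condition is real and is absent from the SAP list, but the listed diary fields give no bleed end time, and the documents give no basis for the direction or size of any effect.

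**Conclusion.** The point holds for the post-injection window. SAP 4.5 enforces the protocol's 72-hour condition and omits its 15-30 minute condition, so a late post sample enters the recovery and FVIII-level summaries as valid under a stated rule.

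The likely effect is small: about 2-4% on a single value sampled at 1 hour and about 5-12% at 2 hours. Visit means move by a few percent at most unless many samples are late or the delays are long. These sizes rest on an assumed half-life of 8-20 hours and mono-exponential decline. How often samples will be mistimed cannot be known from the documents. No primary or secondary endpoint is affected. This is an inexpensive improvement to the SAP and does not threaten the study's conclusions.

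**What to change.** Add one condition to the SAP 4.5 list: a recovery is not valid if the post-infusion sample was taken outside the protocol's 15-30 minute window after the end of injection, with any tolerance fixed before database lock. Derive the interval from the CRF times, and state which recorded injection time marks the end of injection.

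Treat recoveries whose infusion time was imputed under SAP 4.3 as not verifiable for this check, and say in advance whether they stay in the summaries. List excluded pairs with their actual sampling times, alongside the existing listing of FVIII levels invalid for recovery.

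For bleeding, mark in the listing any pair sampled on a calendar day with a diary bleed onset. Do not make an ongoing bleed a programmed exclusion unless a proxy is defined first.

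The cost is a few lines of SAP text, one programmed check on CRF times and one listing flag. The downside is that a few recoveries may move from the summary to the listing.
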